- Aim 2: Develop an evidence-based intervention to reduce head impact exposure in youth football practices, using a community-engaged approach.
- *Aim 3:* Pilot-test the evidence-based practice structure to reduce head impact exposure and mitigate changes in clinical outcomes in youth football.

We **hypothesize** that (a) determinants at the individual (athlete), interpersonal (team & coach), and community levels (built & social environment) of the social ecological model⁸⁴ may be identified and targeted to reduce head impact exposure in youth football practices, and (b) an evidence-based strategy to reduce head impact exposure in practices may be developed and pilot tested using a community-engaged approach. (c) The reduction in exposure will be associated with a lower rate of change in pre- to post-season clinical outcome measures and cognitive function scores.

Methods and Measures

Design

Two local youth football teams at the middle school level (ages 11-14) will be recruited to participate in this study. Informed consent and signed assent forms will be obtained from parents/legal guardians of participating youth football players. All interested football players on the 2 teams will be enrolled; of those enrolled, 15-20 per team (n=30-40 total) will be randomly selected for instrumentation with head impact sensors using a random numbers table. Head impact sensors embedded in a custom mouthpiece will be used to collect head impact exposure in conjunction with on-field video data for a season. These data will be used to inform guided discussions with stakeholders (parents, coaches, league officials). Using an audit and feedback approach (sharing biomechanical data with the stakeholders), we will facilitate semi-structured focus groups with the coaches (n=8) and parents (n=10) of the participating teams, and key informant interviews with league officials (n=8), to assess the awareness and receptivity to creating a safer practice structure. Participants will be asked to complete a series of cognitive, vestibular/ocular motor, and postural stability tasks pre- and post-season.

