An anonymous survey concerning knowledge, attitudes, and practices as well as the perceived needs, perceived benefits, capacity, and barriers to implementing efforts to improve head impact safety will be created and sent to coaches, parents, and league officials (n=153). Data will be combined with published literature to inform the development of an evidence-based intervention using a community-engaged approach. At the end of year 3, two youth football teams at the middle school level will be recruited to pilot test the intervention developed in this study. The football coaches of each team will be prospectively recruited and enrolled. Informed consent will be obtained from adults (coaches and parents/legal guardians of youth athletes) and parents/legal guardians of all participating youth athletes will sign assent forms. Again, all interested athletes on these teams will be enrolled; of those enrolled, 15-20 per team (n=30-40 total) will be randomly selected for instrumentation with head impact sensors using a random numbers table. Athletes will also complete the series of cognitive, vestibular/ocular motor, and postural stability tasks pre- and post-season. On-field activity, skills, and behaviors will be monitored with head impact sensors and on-field video data to evaluate the effectiveness of the intervention at reducing head impact exposure and the acceptability, feasibility, and fidelity of the intervention. The results will be disseminated to the youth football league at the end of the study.

Setting

Biomechanical data collection will occur during youth football practices and games. Stakeholder meetings and key informant interviews will be conducted at the local elementary school, community centers, and Biotech Place in Winston Salem, NC. Clinical outcome data collection and data analysis will be conducted at the WFU Center for Injury Biomechanics, a research lab located at Biotech Place. Additionally, we plan to recruit individuals across the Piedmont Triad and Charlotte Mecklenburg regions in Fall 2024 data collection.

Subjects selection criteria

• Inclusion Criteria

Mouthpiece and Clinical Outcome Data Collection:

All athletes participating on the prospective teams will be eligible for the study, including those with braces longer than 6 months.

Focus Groups, Key Informant Interviews:

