Together with the stakeholders, [name] will conduct monthly stakeholder meetings to develop an intervention focused on reducing head impact exposure in practice. During the first meeting, stakeholders will be gathered for a presentation of research findings, including identified high-risk activities and skills and results from focus groups, interviews, and surveys, and discussion of needs. concerns, and implications of the research using a community-engaged approach. We will conduct Intervention Mapping through three monthly stakeholder meetings to define, develop, refine, and select a strategy to test for reducing head impact exposure in practices. 91 This will include specifying an action-oriented objective and clearly defining which determinants and level(s) of the social-ecological model will be targeted. Together, we will brainstorm possible methods to achieve the defined objectives. The research team will evaluate the level of evidence to support the proposed methods and work with the stakeholders group to translate proposed methods into strategies. Strategies will be developed and compiled to address the identified level(s) of the social ecological model and program objectives. The strategy selected for pilot testing will be determined by the potential to reduce head impact exposure in practices, alignment with needs of the community, feasibility, acceptability, availability of resources (i.e., coaching staff, tackling dummies), and amount of evidence to support the strategy. Acceptability will be a priority when selecting the strategy as guided by Conceptual Model of Implementation Research, which will be used to develop the implementation plan.⁹² Once the strategy has been selected, we will work with stakeholders to operationalize the approach into discrete components with a clear plan of action and programmatic materials. The safety of the participants will be the utmost priority in the development and testing of the intervention.

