Triggers refer to the standards an athletic trainer or coach will use to determine whether or not an impacted player should receive further testing. The triggers for testing will be the standard already used by the athletic trainers and will not be altered due to this study. If a concussion is suspected, the athletic trainers typically use the SCAT5 on-field to determine whether to remove an athlete from play. Following removal from play, the athletic trainers use the SCAT5 to assist with a clinical diagnosis of concussion which would trigger further testing. Athletic trainers and physicians will follow normal methods for diagnosis and treatment of a concussion and not be restricted to only the information found in this protocol.

Post-Injury Testing:

Post-injury testing is any testing that is administered after a player has been diagnosed by a team physician or athletic trainer to have a concussion. The records for Post-Injury Testing will only be provided and used for research analysis AFTER a concussion has been diagnosed, pending signed authorization by the players on the Informed Consent document. No additional or different testing will be done because of a player's participation in the study.

Post-injury testing will include baseline cognitive, postural control, and vestibular/ocular motor testing within 24-48 hours after concussion diagnosis.

Outcome Measure(s)

- Primary Outcomes:
 - o Number of head impacts, impact rate
 - Mean and 95th percentile number of impacts, linear acceleration, rotational acceleration by session type, activity, skill and behavior
 - Pre- to Post-Season change scores for:
 - ImPACT
 - NIH Toolbox
 - RAVLT
 - Postural Control
 - VOMS
 - Conners' CPT
- Secondary Outcomes:
 - Implementation facilitators and barriers
 - Intervention fidelity
 - Adaptation of the intervention

Analytical Plan

Statistical analysis of biomechanical data will be based on our previous approaches.^{9,11,64} Head impact data will be transformed to the head center of gravity using Matlab (Mathworks, Inc., Natick, MA) and quantified for each session (i.e., practice or game) and practice drill category (i.e., conditioning, tackling) and across drill types (i.e., Oklahoma, one-on-one) in terms of mean number of impacts and impact rate and mean and 95th percentile head acceleration.

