On-field head impact data for each athlete will be quantified for each practice or game by number of impacts, impact rate, mean, median, and 95th percentile of head acceleration, and location of impact. Impact rates and percentiles (i.e., 50th, 95th) computed from the distribution of accelerations will be compared between unexposed (year 2, published iTAKL and BRP study data^{61,106–108}) and exposed seasons of data collection. Mixed-effects models (in SAS) will be used to assess differences in head impact exposure in practices and games before (year 2, published iTAKL and BRP study data^{61,106–108}) and after the intervention, adjusting for confounding factors, including team. We will examine the consistency of intervention effects on exposure outcomes between teams and among players over time, with the goal of learning how to refine and tailor the intervention to increase adherence and potential effectiveness. Because this is a pilot study, we will lack sufficient power to fully test the effectiveness of the intervention; however, we will gather essential information for a future R01-supported randomized control trial.

All clinical assessment scores will be compared to same age peers at testing time (via published normative values) to control for developmental changes that may occur during the study period. Scores will be normalized (i.e. z-scores) to facilitate comparisons among cognitive tests. Kinematic metrics (i.e., total impacts, 95th percentile accelerations and rotational velocity, RWE) will be time-varying covariates in generalized linear and mixed effects models. The modeling framework, with its random effects structure, will allow for assessment of clinical outcome differences pre- to post-season over time between the intervention athletes and controls. We will also describe whether associations may vary according to athletes' characteristics.

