Descriptive data and inferential statistics related to implementation facilitators and barriers (i.e., feasibility, acceptability), fidelity (i.e., extent to which the intervention was implemented as prescribed), and adaptation (i.e., changes) of the intervention will be analyzed. These data will be abstracted from standardized forms collected during on-field observations, video-analysis of practices and games, and brief surveys and field notes from stakeholder feedback meetings. Common themes will be grouped, and qualitative data indexed and charted. These data will be analyzed to assess the degree to which the practice structure was effective at reducing head impact exposure, was adopted by the youth football coaches, and to identify the key components of the strategy that may be implemented and sustained over time.

Human Subjects Protection

Subject Recruitment Methods

[name] will work with the league executive board to arrange meetings for coaches, parents, and players to describe the study and provide opportunities to answer questions. She and study personnel will also attend pre-season conditioning sessions to meet with parents, coaches, and athletes not present at the meetings. Those not present at the meetings or pre-season conditioning sessions will be sought out individually by phone for their interest in participating in the study. All interested athletes on these teams will be allowed to participate; of those enrolled, 15 children on each team will be randomly selected for instrumentation with head impact sensors using a random numbers table. Coaches and parents of the participating teams will be recruited to participate in separate focus groups and league officials will be prospectively recruited to participate in key informant interviews. A new set of football coaches and teams will be prospectively recruited and enrolled in the intervention portion of this study using similar recruitment strategies as the controls. Informed consent will be obtained from adults (coaches, parents, and league officials) and parents/legal guardians of all youth athletes and participating athletes will sign consent and assent forms.

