To maintain a robust cohort of subjects, we will enroll all interested subjects from each team for possible participation in the study and randomly choose 15 per team for study at the start of the season. Participation will be monitored weekly; if an athlete has attended 50% or less of the practices or games within a 3 weeks, a new subject who enrolled prior to the start of the season will be randomly chosen for biomechanical data collection and given a sensor. We anticipate a possible attrition rate of 15% based on experience from our existing R01s. To ensure that sufficient participants are included, we will work closely with the local youth football league to identify and engage additional teams, if needed.

To reward all subjects for attending appointments to complete baseline, post-injury, and post-season evaluation procedures during the contact sport seasons, a gift card will be awarded, at all appointments, for the subject's additional travel and time to attend the procedures. See the table below for gift card compensation amounts.

Neurocognitive Testing	Dental Impressions + Head/Face Measurements	Neurocognitive Testing, Impressions, Head/Face	Dental +
		Measurements	

Pre-season/baseline	\$20	\$20	\$40
Post-injury	\$20	N/A	
Post-season	\$40	N/A	

To reward all stakeholders for attending all meetings, focus groups or key informant interviews, a gift card will be awarded, at all appointments, for the additional travel and time to attend the meetings. See the table below for gift card compensation amounts. To encourage participation, participants enrolled in the focus groups and key informant interviews will be entered into a raffle for four Wake Forest Football Tickets. All focus group and key informant interview participants enrolled in the study at the time of the raffle will be eligible to win. Winner will be selected using a random numbers table.

	Focus Groups	Key Informant Interviews	Stakeholder Meetings	Athlete Stakeholder Meetings
Compensation for each meeting	\$20	\$20	\$20	\$20
Number of meetings	4	2	18	4
Total compensation*	\$80	\$40	\$360	\$80

*if all meetings are attended

The gift card will be given to the subject at the time of the meeting. A record confirming receipt by the subjects of the gift card will be kept.

Informed Consent

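### The before/after exposure model lists team as a confounder to adjust for, but the pilot uses new teams: the effect can only be a between-team contrast and should be analysed and labelled as one

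*Combined protocol and SAP*

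**What the plan says.** The Analytical Plan assesses exposure in practices and games with mixed-effects models, before "and after the intervention, adjusting for confounding factors, including team". On the unexposed side, impact rates and percentiles "will be compared between unexposed (year 2, published iTAKL and BRP study data" with those of the exposed seasons, and the mixed model uses the same comparator. Team is not labelled fixed or random, and no denominator degrees of freedom are given. The section opens by pointing elsewhere: "Statistical analysis of biomechanical data will be based on our previous approaches".

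On who is compared, the Design section says of the control season: "Two local youth football teams at the middle school level (ages 11-14) will be recruited to participate in this study". Of the pilot, at the end of year 3, it says: "two youth football teams at the middle school level will be recruited to pilot test the intervention developed in this study". Subject Recruitment Methods adds: "A new set of football coaches and teams will be prospectively recruited and enrolled in the intervention portion of this study", with recruitment similar to that of the controls. The number of teams may grow: "we will work closely with the local youth football league to identify and engage additional teams, if needed".

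The Analytical Plan concedes that the pilot is underpowered for effectiveness and leaves that question to a later randomized trial.

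**The concern.** Adjusting for a confounder requires it to vary within each condition, or each of its levels to be seen under both conditions. Here every team appears to be wholly unexposed or wholly exposed, so team is nested in condition. The Intervention Summary delivers the programme through coaches (clinic, practice plans, booklet, peer mentor), so team is also the unit that receives it.

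An estimate described as adjusted for team would be read as free of team differences. This design cannot provide that. The contrast is the plan's inferential look at whether exposure fell, and it is meant to inform a randomized trial, so a misleading label would carry forward.

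**Working it through.** **The plan's own figures.** No power or precision is given for the before/after comparison. The Sample Size section gives two other figures for N=30, and both reproduce:
- Power for r = 0.50 (two-sided 5% assumed): Φ(atanh(0.5)·√27 − 1.96) = Φ(2.854 − 1.960) = 0.814, above 80%.
- 90% interval for an SD: √(29/χ²) on 29 df = 0.825 to 1.280, against the stated 0.83 to 1.28.

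Neither figure involves teams.

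**Inputs.** Two control and two pilot teams (Design). Fifteen instrumented athletes per team (Intervention section; Design says 15-20). Assumed, because the documents do not give them: intraclass correlation (ICC) 0.02 to 0.20, one season value per athlete, and team counts beyond 2+2.

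**Step 1: team fixed.** With c control and i intervention teams, none shared, the model has an intercept, c+i−1 team indicators and an intervention indicator: c+i+1 columns. The intervention column is a linear combination of the intercept and team columns, so the rank is c+i.

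| Teams (control + intervention) | Columns | Rank |
|---|---|---|
| 2+2 | 5 | 4 |
| 4+2 | 7 | 6 |
| 4+4 | 9 | 8 |
| 8+2 | 11 | 10 |

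The rank is always one short, so further non-overlapping historical teams do not help. If the same two teams were seen in both conditions, the rank would be full (3 of 3). With one shared team among three it is also full (4 of 4). The cause is the use of new teams.

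Season behaves the same way. With year 2 as the study's only control season, intercept + intervention + season is 3 columns of rank 2.

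**Step 2: team random.** The effect is now estimable from team means. In units of the total athlete-level SD:

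SE = √[(ICC + (1−ICC)/15)·(1/c + 1/i)], df = c + i − 2.

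For 2+2 teams the last factor is 1, df = 2 and t = 4.30:
- ICC 0.02: SE = √0.0853 = 0.292; half-width 4.30 × 0.292 = 1.26
- ICC 0.05: SE = √0.1133 = 0.337; half-width 1.45
- ICC 0.10: SE = √0.1600 = 0.400; half-width 1.72
- ICC 0.20: SE = √0.2533 = 0.503; half-width 2.17

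With no team level: 2.00 × √(1/30 + 1/30) = 0.52.

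The detectable difference at 80% power comes from the noncentral t distribution:

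| Teams | df | 95% half-width, ICC 0.02 to 0.20 | Detectable at ICC 0.02 / 0.05 / 0.10 / 0.20 |
|---|---|---|---|
| 2+2 | 2 | 1.26 to 2.17 | 1.65 / 1.90 / 2.26 / 2.85 |
| 4+2 | 4 | 0.70 to 1.21 | 0.95 / 1.10 / 1.30 / 1.64 |
| 4+4 | 6 | 0.51 to 0.87 | 0.70 / 0.80 / 0.95 / 1.20 |
| 8+2 | 8 | 0.53 to 0.92 | 0.74 / 0.85 / 1.01 / 1.27 |

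More athletes per team help little: with 20 per team in 2+2 and ICC 0.20, the half-width is 2.11 rather than 2.17.

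**Step 3: what the random term does.** It moves between-team variation into the standard error. It does not shift the point estimate towards what the same teams would have shown without the intervention. Differences in coach, season and data source remain in the estimate.

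**The case against.** The strongest reply is that the plan specifies mixed-effects models and never says team is fixed. On the natural reading team is random and the model can be fitted. That stands: a reader might infer from the rank result that the planned analysis cannot be run, and the documents do not support that. What remains is that a fittable random term does not adjust for team as a confounder.

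Second, a reader might infer that athletes will be tested as independent, with an inflated false-positive rate. The plan does not propose leaving team out, so such error rates describe an analysis nobody has planned and are not evidence of harm here.

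Third, non-overlap is not fully settled. The teams are new relative to the controls; the documents do not identify the iTAKL and BRP teams or say whether an intervention team was among them. The conclusion is therefore conditional. The earlier approaches that the plan cites may specify a team structure, but they cannot supply a team observed in both conditions.

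Fourth, this is an admitted pilot that already plans to look at consistency of effects between teams. That covers part of the descriptive reporting. The power caveat, however, concerns imprecision, whereas confounding is bias.

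Finally, a reader might infer that comparing practices with games rescues the design, since stakeholders are "to develop an intervention focused on reducing head impact exposure in practice". That contrast does remove stable team differences. It assumes, however, that practice/game differences do not vary by team and that the intervention leaves game exposure unchanged. The second assumption is doubtful: the Intervention Summary also targets attitudes to contact, and the plan assesses games too. If game exposure also falls, the contrast is biased toward zero.

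**Conclusion.** The concern holds, on the condition that no team appears in both conditions, which is what the recruitment text plans. The stated adjustment then either cannot be fitted (team fixed) or does not remove team differences (team random). In the 2+2 design the honest 95% half-width is 1.26 to 2.17 SDs against 0.52 with no team level, and the detectable difference is 1.65 to 2.85 SDs. These sizes rest on the assumed ICC range and 15 athletes in every team. Extra unexposed teams narrow the interval but leave the confounding.

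This does not make the pilot invalid. The analysis should be described as what it is, and this is worth correcting before the exposure analysis is run. Sensor type, the exposure status of the Fall 2022 and Fall 2024 athletes, and the use of summary-only historical data are separate matters.

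**What to change.** In the Analytical Plan, replace adjustment for team as a confounder with:

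> Team is a random effect with athletes nested in team. The intervention is a between-team factor tested with between-team degrees of freedom (number of independent teams minus 2 if no team appears in both conditions; seasons of a returning team are treated as paired). The estimate is reported as confounded with team, coach, season and data source, alongside team-specific rates.

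If a practice-minus-game contrast is also reported, state both of its assumptions: no team-specific practice/game difference, and no effect of the intervention on game exposure.

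The cost is one model statement and one reporting sentence, with no new data. The downside is wider intervals. With 2+2 teams the comparison becomes mainly descriptive, which fits the low power the plan already acknowledges.

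### On its natural reading, the clinical intervention-versus-control contrast is conditioned on head-impact exposure, the intended pathway, and no clinical model without kinematics is described

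*Combined protocol and SAP*

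**What the plan says.** Aim 3 (Objectives) is to pilot-test a practice structure to "reduce head impact exposure and mitigate changes in clinical outcomes in youth football". Hypothesis (c) in the same section reads: "The reduction in exposure will be associated with a lower rate of change in pre- to post-season clinical outcome measures". The Intervention Summary gives fewer head impacts as what the intervention tries to achieve. Outcome Measure(s) lists pre- to post-season change in the clinical tests among the primary outcomes.

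The Analytical Plan has one paragraph on modelling the clinical scores. After comparison with published norms and conversion to z-scores, it says that the kinematic metrics (total impacts, 95th percentile accelerations and rotational velocity, RWE) "will be time-varying covariates in generalized linear and mixed effects models". The next sentence says that the modelling framework will "allow for assessment of clinical outcome differences pre- to post-season over time between the intervention athletes and controls". The paragraph closes by turning to whether associations vary with athlete characteristics.

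The preceding paragraph describes a different mixed model, with head-impact exposure as the outcome, "adjusting for confounding factors, including team". The clinical paragraph names no such adjustment. The same section says that the pilot lacks power to test effectiveness fully, but that "we will gather essential information for a future R01-supported randomized control trial".

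**The concern.** Season kinematics are recorded after the intervention has begun and are the quantity it is designed to lower. They are therefore a mediator, not a baseline confounder. A group coefficient fitted alongside them leaves out whatever part of the effect runs through exposure. Even as a direct effect it needs exposure and outcome to have no unmeasured shared causes.

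Aim 3 implies interest in the overall difference in clinical change between intervention athletes and controls. If the only group contrast reported is exposure-adjusted, a successful intervention working as intended could show a small coefficient, and that coefficient could be carried into the planning of the later trial as if it were the intervention's clinical effect.

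**Working it through.** **The plan's own figures.** No clinical effect size or power is given. The Sample Size section offers two figures for N=30, and both reproduce. Power for r=0.50 (two-sided 5% assumed): Φ(atanh(0.5)·√27 − 1.96) = Φ(2.854 − 1.96) = 81.4%, against a stated value above 80%. The 90% interval for an SD: √(29/χ²) with 29 degrees of freedom gives 0.825 to 1.280, against 0.83 to 1.28. Neither bears on which contrast is estimated.

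**What the text supports, step by step.**
1. Intervention to exposure: Intervention Summary.
2. Exposure to clinical change: hypothesis (c).
3. Exposure metrics as covariates in the clinical models: Analytical Plan.
4. Group difference taken from that framework: Analytical Plan, next sentence.
5. A clinical group model without exposure: none found. The other mixed model has exposure as its outcome.

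**Illustration (every effect input is assumed).** Let G be group, M exposure and Y clinical decline, with M and Y scaled to a within-group variance of 1:
- M = −d·G + error, with d = 1
- Y = b·M + c·G + error
- overall effect = c − b·d = −0.50
- for mediated share s: b = 0.5·s and c = −0.5·(1 − s)

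Written as a benefit, the contrast without M is 0.50 and the contrast with M is 0.50·(1 − s). The two agree only when b·d is near zero. The standard error without M is √(2/n). With M it is about √((1 − b²)(2/n + 1/(2n − 4))), for n per group. From the protocol, n = 30 is two teams of 15, n = 40 is two teams of 20, and n = 26 is 30 less 15% attrition (30 × 0.85 = 25.5, rounded up).

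| Mediated share | Contrast without M | Contrast with M | SE with M, n=26 | SE with M, n=30 | SE with M, n=40 |
|---|---|---|---|---|---|
| 100% | 0.50 | 0.00 | 0.27 | 0.25 | 0.22 |
| 50% | 0.50 | 0.25 | 0.30 | 0.28 | 0.24 |
| 25% | 0.50 | 0.375 | 0.31 | 0.29 | 0.25 |
| near 0% | 0.50 | about 0.50 | 0.31 | 0.29 | 0.25 |

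The standard error without M is 0.28, 0.26 and 0.22 at n = 26, 30 and 40. For example, at n = 30 and s = 100%: √(0.75 × (0.0667 + 0.0179)) = 0.252.

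A simulated two-visit random-intercept model at n = 30, with kinematics set to 0 before the season and to the season value after it, gave group-by-time estimates of 0.50/0.50/0.51 without kinematics and 0.00/0.25/0.38 with them, for 100/50/25% mediation.

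For scale, the 95% half-width without kinematics at n = 30 is about 1.96 × 0.258 = 0.51 SD, before any allowance for team clustering. The shift is systematic, but in one pilot it is no larger than the sampling uncertainty.

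**The case against.** **The joint fit is inferred.** A reader might infer that the plan commits to one model holding both group and kinematics, and so to a wrong analysis. The documents do not support that. They speak of models in the plural, across two families, and write no equation. Separate exposure-outcome models for hypothesis (c), with a group-by-time comparison in the same general framework, would fit the wording. What stands is that no such separate comparison is described.

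**A small adjusted contrast could still be interpreted.** A reader might infer that the results could not separate no clinical effect from an effect acting through exposure. That goes too far. The planned exposure model estimates d, the kinematic coefficient estimates b, and the adjusted contrast estimates c. A small c with b and d near zero reads differently from a small c with both clearly non-zero. But the exposure comparison also draws on published data from other studies, several kinematic metrics are planned, and no step combines the pieces into an overall estimate.

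**The overall effect is not defined as the target.** Aim 3 implies it, but neither the aim nor the outcome list states it, and kinematics are the right predictor for hypothesis (c). This is fair, and it is a reason to add a contrast rather than remove the kinematic models.

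**Exposure may hardly matter over one season.** Background, Rationale and Context notes that some studies found no strong and consistent link between playing football and cognitive change after a season. In that case the two contrasts nearly coincide, as the last row of the table shows. The same section links pre-season physical performance to exposure but not to clinical scores, so confounding by shared causes is possible and not demonstrated.

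**The illustration is simplified.** It uses the same n for both contrasts, one error-free metric and no team effects. It omits the Fall 2022 and Fall 2024 cohorts and the replacement of low-attending athletes.

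**The pilot caveat.** It concerns power and does not settle which quantity is estimated, but it does lower the stakes.

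**Conclusion.** The point holds as a gap in specification with a foreseeable consequence. As naturally read, the clinical group contrast is conditioned on the intended pathway. It is then at most a direct effect, and the plan provides no overall estimate. With an assumed 0.50 SD overall effect, the loss ranges from all of it (full mediation) through 0.25 and 0.125 SD (50% and 25%) to almost nothing (mediation near zero). These figures rest on assumed values for effect size, exposure shift and mediated share, because the documents supply none.

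Severity is low to moderate, given the pilot purpose and the ambiguous text. A reader might also infer that dropping the kinematics would isolate the intervention effect. It would not. The Design section, describing the later recruitment phase, says that "two youth football teams at the middle school level will be recruited to pilot test the intervention developed in this study", and Subject Recruitment Methods says: "A new set of football coaches and teams will be prospectively recruited and enrolled in the intervention portion of this study". The comparison is therefore non-concurrent, and team and season cannot be separated from intervention.

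**What to change.** 1. State that the intervention-versus-control contrast, for each clinical measure actually collected both pre- and post-season, comes from a model with group, time, group-by-time, random effects and pre-season covariates only, without kinematics. Fit it in all clinically tested athletes, since only 15-20 per team carry sensors. Report it as an estimate with a confidence interval, and describe it as a non-concurrent comparison in which team and season cannot be separated from intervention.
2. Before including ImPACT, reconcile Neurocognitive Assessments, where it is given after a concussion diagnosis, with Outcome Measure(s), which lists its pre- to post-season change.
3. Keep the kinematic models as separate exposure-outcome analyses for hypothesis (c) in instrumented athletes, and state that a group coefficient in them is not the overall intervention effect.

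The cost is SAP wording and one extra model per clinical outcome, with no new data. The downside is that the added estimate remains confounded by team and season.
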